3.4 Primary Safety Endpoints

Safety of the technique will be assessed by MRI and neurocognitive tests, to guarantee that FUS-induced BBB opening at low frequency and pressure does not cause adverse effects in patients.

4 Subject Selection and Withdrawal

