8.1 Definitions

Unanticipated adverse device effect (UADE): Any serious adverse effect on health or safety or any lifethreatening problem or death caused by, or associated with, a device, if that effect, problem, or death was not previously identified in nature, severity, or degree of incidence in the investigational plan or IDE application (including a supplementary plan or application), or any other unanticipated serious problem associated with a device that relates to the rights, safety, or welfare of subjects.

Associated with the investigational device: There is a reasonable possibility that the adverse effect may have been caused by the investigational device.

Life-threatening adverse effect: Any adverse effect that places the subject, in the view of either the investigator or the sponsor, at immediate risk of death from the effect **as it occurred**. It does not include a reaction that, had it occurred in a more severe form, might have caused death.

Serious adverse effect: An adverse effect is considered "serious" if, in the view of either the investigator or the sponsor, it results in any of the following outcomes:

- death
- a life-threatening AE
- inpatient hospitalization or prolongation of existing hospitalization
- a persistent or significant disability/incapacity
- a congenital anomaly/birth defect.

Unanticipated adverse effect: Any adverse effect, the nature, specificity, severity, or frequency of which is not consistent with the risk information in the clinical study protocol or elsewhere in the current IDE application.

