8.3.2 Investigator reporting: *Notifying the IRB*

ALL unanticipated adverse device events will be reported immediately and no later than within 2 business days to the IRB committee, regardless of seriousness or severity. Unanticipated problems involving risks to subjects and others will be recorded and reported to IRB within 5 business days. Expected or unrelated adverse effects and potential protocol violations will be recorded and reported in our annual progress report.

Any suspension or terminations of IRB approval will be reported to NIMH no later than within **3 business days of receipt**. Unanticipated adverse effects or serious adverse events will be reported to NIMH no later than within **10 business days** of the study team becoming aware of the event.

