8.5 Stopping Rules

Redundant safety features have been added to the hardware of the device, as grounding for the transducer, safety switch for the amplifier and function generator. Additionally, we will incorporate safety valves in our software. For any signs showing safety risk including high cavitation dose in the acoustic monitoring or unstable vital signs, the device can be stopped from the computer user interface and/or an emergency stop button. Treatment will be stopped in the case of any reaction of the subject to the ultrasound exposure or microbubble infusion. Pulse oximetry will be used during MRI scans to mitigate the risk of anaphylactic reaction to MRI contrast agents. Potential adverse effects have been grouped according to their severity in the following table:

Severity	Adverse effect			
Severe	Local hemorrhage	Edema	Intracranial infection	Status epilepticus
Moderate	Emesis	Dizziness	Allergic reaction	Nausea
Mild	Skull heating	Injection site bruising	Headache	

The investigation will be paused and the relevant authorities will be notified in case of any death, life threatening event, or any other serious adverse event described in the table above (including disability or clinically significant manifestation of local hemorrhage or edema) due to the procedure. An episode of status epilepticus during treatment will terminate the session immediately.

If the selected ultrasound settings (i.e., MI of 0.4) do not successfully open the BBB in 3 subjects, FDA will be contacted via a submission of an IDE supplement, to discuss revising the protocol's focused ultrasound parameters or increase the number of subjects.

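### The 8.5 pause trigger does not map to the 8.1 definition of serious, conflicts with 8.6, and leaves expected serious events to the annual IRB report

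*Combined protocol and SAP*

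**What the plan says.** **Pause rule (8.5).** The section first introduces a table: "Potential adverse effects have been grouped according to their severity in the following table". Its rows are Severe (local hemorrhage, edema, intracranial infection, status epilepticus), Moderate (emesis, dizziness, allergic reaction, nausea) and Mild (skull heating, injection-site bruising, headache). The rule then reads "The investigation will be paused and the relevant authorities will be notified in case of any death, life threatening event". Its remaining limb covers "any other serious adverse event described in the table above (including disability or clinically significant manifestation of local hemorrhage or edema) due to the procedure". The same section stops treatment if the subject reacts to the ultrasound or the microbubbles, and ends the session for status epilepticus during treatment.

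**Seriousness (8.1).** An effect is serious if "in the view of either the investigator or the sponsor, it results in any of the following outcomes": death, a life-threatening event, "inpatient hospitalization or prolongation of existing hospitalization", "a persistent or significant disability/incapacity", or a congenital anomaly. Section 8.2 also ties seriousness to outcome.

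**Other halting text (8.6, 8.6.1).** Both sections discontinue the study at once for an allergic or any other reaction to the therapy. Section 8.6 gives status epilepticus as an example.

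**Reporting (8.3.2, 10.1).** Unanticipated device events go to the IRB within 2 business days whatever their seriousness, and unanticipated problems within 5. Otherwise, "Expected or unrelated adverse effects and potential protocol violations will be recorded and reported in our annual progress report". Unanticipated effects and serious events go to NIMH within 10 business days. Section 10.1 makes the IDE holder responsible for safety reports to the FDA and the IRB as needed, with no time limit.

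**Safety endpoint (3.4).** "Safety of the technique will be assessed by MRI and neurocognitive tests".

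**The concern.** Severe and serious are different scales. Severity grades the intensity of an event, and seriousness, as 8.1 defines it, depends on what the event leads to. Section 8.5 uses the term serious but points to a severity table for its content, and its own example, disability, is not in that table. The person applying the rule has to guess which scale governs. A second set of halting words in 8.6 and 8.6.1 uses neither scale, and the IRB route in 8.3.2 turns on a third attribute, expectedness.

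This matters because the study treats six subjects in an early safety and feasibility setting, and 8.6.1 describes no independent committee. Every subject has MRI on the day of sonication and again about three days later, and MRI is one of the two instruments for the primary safety endpoint. A finding visible only on MRI is exactly what this design is built to detect. If the text does not settle its consequence in advance, the decision will be made after the event has been seen.

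**Working it through.** The plan gives no figure to reproduce and no arithmetic applies beyond counting. The check reads 8.1, 8.3.2, 8.5, 8.6, 8.6.1 and 10.1 side by side and follows example events through them. All are assumed to be due to the procedure, because 8.5 requires that. It follows that the unrelated limb of the annual-report sentence drops out and only the expected limb matters.

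| Event | Serious under 8.1? | Pause under 8.5? | 8.6 / 8.6.1 | IRB timing under 8.3.2 |
|---|---|---|---|---|
| A. Admission for chest pain after the microbubbles, not life-threatening or disabling | Yes | No on the literal text: not in the table | Study discontinued, if a reaction to the therapy | Annual if judged expected (1.5.1 names it as a known side effect); 2 business days if unanticipated |
| B. Admission for an allergic reaction | Yes | Yes on the literal text: serious and in the table | Study discontinued | Annual if expected; 2 business days if unanticipated |
| C. Clinically significant hemorrhage with admission | Yes | Yes, with notice to unnamed authorities | Study discontinued, if a reaction to the therapy | Annual if expected; 2 business days if unanticipated |
| D. Hemorrhage or edema on MRI only | No 8.1 outcome | Unclear: Severe in the table without qualification, but the rule names only a clinically significant manifestation, undefined | Unclear whether this is a reaction; 8.6 also withdraws the subject for incidental findings | Annual if expected; 2 business days if unanticipated |
| E. Status epilepticus during treatment | Depends on outcome | Session ends; pause if life-threatening or serious | Study discontinued | Annual if expected; 2 business days if unanticipated |

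Events A, B and C also go to NIMH within 10 business days because they are serious.

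**Coverage of the 8.1 outcomes.** There are five. Section 8.5 names three itself (death, life-threatening, disability). The other two, hospitalization and congenital anomaly, are reached only if the event is in the table. Hospitalization is the one with practical weight, since pregnancy is an exclusion.

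**Coverage of the Severe row.** There are four entries. Hemorrhage and edema depend on the undefined qualifier. Status epilepticus ends the session in 8.5 but the study in 8.6. That leaves 3 of 4 with an unsettled consequence.

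**Can a pause-triggering event be judged expected?** Section 8.1 makes an effect unanticipated if its nature, severity or incidence was not identified beforehand. The 8.5 table identifies hemorrhage, edema and status epilepticus and grades them Severe, and 1.5.1 names hemorrhage and edema as possible at high intensity. That supports expected. Section 1.5.1 also says that no damage has been reported at low intensity, and links hemorrhage to relatively high pressures. That supports unanticipated at the planned MI of 0.4. Both classifications are open on the text, so the IRB clock for the same event is either 2 business days or the next annual report.

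**The case against.** The strongest case on the other side is that the 8.5 wording is loose but workable, and that other sections cover most of the gap.

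- **Halting.** A reader might infer that 8.5 is the only rule that stops further sonications. It is not. Sections 8.6 and 8.6.1 discontinue the study for any reaction, with no threshold, and on their face they catch events A, B and E. This stands. It narrows the gap but creates a contradiction, because 8.5 stops only treatment for any reaction. If study in 8.6 means the session, the text does not say so.
- **Reporting against halting.** A reader might also infer that 8.3.2 cancels the pause, so that one event both does and does not halt. It cannot, because 8.3.2 governs reporting only. On halting, the fault lies within 8.5 and between 8.5 and 8.6.
- **Moderate-row events.** It is tempting to say that these escape the pause. They do not. An allergic reaction that leads to admission is serious and is in the table. The rule never mentions the Severe row.
- **MRI-only findings.** Two tests point to no pause: there is no 8.1 outcome, and a silent finding is not clearly clinically significant. That is the more natural reading, but the qualifier is undefined and the table grades these findings Severe without it.
- **Delay.** A year's wait for the IRB is the worst case and applies only if the event is judged expected. Serious events reach NIMH within 10 business days, and 10.1 promises IDE safety reports. This stands too, but NIMH is not the IRB, and 10.1 sets no deadline.

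**Conclusion.** The point holds in a limited form. Three defects are in the text. First, the 8.5 trigger leaves a procedure-related hospitalization for an unlisted, non-life-threatening, non-disabling event outside its literal words, and leaves MRI-only hemorrhage or edema unclear. Second, 8.5 conflicts with 8.6 and 8.6.1 on whether a reaction, and status epilepticus in particular, ends treatment, the session or the study. Third, the annual-report sentence in 8.3.2 has no exception for an expected event that is serious or triggers the pause, while 8.5 promises notice without naming recipients or a time.

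The third defect rests on the assumption that such an event would be judged expected, which the documents allow but do not require. Whether it contradicts 8.5, rather than merely leaving a gap, depends on the IRB being among the relevant authorities. The documents give no rate for silent MRI findings or for serious events judged expected, so no probability that the conflict will arise can be supported. Nor do they support the inference that all six subjects could be treated after a clinically significant hemorrhage, since 8.5 pauses for that.

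This is still a safety correction rather than a request for more detail. Applied as written, the rules could leave a serious procedure-related event without a pause under 8.5, or without prompt notice to the IRB.

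**What to change.** 1. Reconcile 8.1, 8.3.2, 8.5, 8.6, 8.6.1 and 10.1 so that each type of event has one stated consequence at one stated level (session, subject or study), expressed in the terms of the 8.1 definition. Say explicitly whether a hemorrhage or edema seen only on MRI counts, and define clinically significant if the phrase is kept. Which clinical rule applies is for the sponsor to decide.
2. Amend the annual-report sentence in 8.3.2 so that it does not cover any event that is serious or triggers the 8.5 pause, whether or not it was expected.
3. In 8.5, name the bodies to be notified and the deadline, and align this with the IDE safety reports in 10.1.

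The cost is protocol wording in a few sections and possibly an earlier report to the IRB. No new procedures, visits or data are needed.

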8.6 Medical Monitoring

Medical monitoring will be performed by the neurologist of this study, [name], MD at the Taub Institute of Alzheimer's Disease and Aging at Columbia. [name] or any other trained radiologist will be present during the trial and will assess the subject's clinical status during therapy. In the case of an allergic or any other reaction (e.g. status epilepticus) to the therapy, the study will be immediately discontinued. Resuscitation equipment will be readily available in the study room, in case of a serious adverse event.

Subjects will be monitored with follow-up MRI scans to confirm BBB opening and closing and PET scans to estimate amyloid plaque load. Should the MRI or PET brain scans of this study have incidental findings (e.g. brain tumor, subarachnoid hemorrhage, or structural abnormality) the subject will be immediately withdrawn from the study and directed for clinical care. MRI scans will be examined by [name], who is a certified in Diagnostic Radiology and is the Section Chief of Neuroradiology. MRI scan examination by [name] will occur as soon as possible but no later than two weeks following receipt of the image.

If there are any incidental findings deemed by the clinical-investigator to be "life-threatening" or "important but not severe", both the subject and the subject's personal primary care physician will be notified. Communication may be initially verbal, followed by a formal written communication. The significance of the incidental finding will be determined by the clinical-investigator and communicated to the subject accordingly. Incidental findings of clinical significance and the management of such findings should be documented in the research records of this study.

At the time of a continuing review, if incidental findings were noted during the previous approval period, the principal investigator of this study will provide the IRB with the following information: the number of required review images, a list of the subject study numbers, the type of scan, the date of the scan, a description of the incidental finding of clinical significance, the date of communication with the subject and the outcome, if known.

If the participants expressed severe depression or suicidal ideation in the course of their visit, the subject will be urgently assessed by the study clinician and appropriate referrals will be made. In addition, we will exclude the participant from the study.

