8.2 Recording of Adverse Device Effects

All observed or volunteered adverse effects (serious or non-serious) and abnormal test findings, regardless of treatment group, if applicable, or suspected causal relationship to the investigational device or, if

applicable, other study treatment or diagnostic product(s) will be recorded in the subjects' case histories. For all adverse effects, sufficient information will be pursued and/or obtained so as to permit 1) an adequate determination of the outcome of the effect (i.e., whether the effect should be classified as a serious adverse effect) and; 2) an assessment of the causal relationship between the adverse effect and the investigational device or, if applicable, the other study treatment or diagnostic product(s).

Adverse effects or abnormal test findings felt to be associated with the investigational device or, if applicable, other study treatment or diagnostic product(s) will be followed until the effect (or its sequelae) or the abnormal test finding resolves or stabilizes at a level acceptable to the sponsor-investigator.

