8.6.1 Data Monitoring Committee (if applicable)

The safety of the BBB opening using ultrasound and microbubbles has been confirmed by previous nonhuman primates studies, which revealed no adverse effects, permanent damage, or behavioral change following repeated treatments using low-intensity ultrasound and clinically-relevant microbubble doses. Ongoing clinical trials using this technique have not reported any acute adverse effect in either of the participants. However, long-term effects in the human brain have not been investigated to date.

To ensure the long-term safety in our study, the investigators will monitor and collect the data for processing and analysis while [name] will be present to assess the safety of the patient during FUS application. [name] will be present during the trial and will assess the subject's clinical status during therapy. In the case of an allergic or any other reaction to the therapy, the study will be immediately discontinued. Resuscitation equipment will be readily available in the study room, in case of a serious adverse event. Subjects will be monitored with follow-up MRI scans to confirm BBB opening and closing. BBB opening will be confirmed with an MRI scan immediately after the ultrasound treatment, while BBB closing will be confirmed three days later. Additional clinical evaluation will be performed by [name] or any other trained neurologist 3 months after the ultrasound treatment. Should the MRI brain scans of this study have incidental findings (e.g. brain tumor or potential structural abnormality) the subject will be immediately withdrawn from the study and directed for clinical care. Incidental findings will be communicated with both the subject and the subject's personal primary care physician.

Cognitive function will be assessed by [name] using appropriate tests before, during, and after the treatment.

9 Data Handling and Record Keeping

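### A treated subject withdrawn for a new scan finding labelled incidental could lose later safety data and fall outside the only defined analysis set (7.3)

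*Combined protocol and SAP*

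**What the plan says.** **Withdrawal.** Under section 8.6, study MRI or PET scans that show "incidental findings (e.g. brain tumor, subarachnoid hemorrhage, or structural abnormality) the subject will be immediately withdrawn from the study and directed for clinical care". Section 8.6.1 has the same rule for MRI with a shorter list of examples: "incidental findings (e.g. brain tumor or potential structural abnormality) the subject will be immediately withdrawn from the study". Both give examples and no definition. In 8.6 the rule comes directly after the sentence on monitoring by follow-up MRI and PET. MRI reading "will occur as soon as possible but no later than two weeks following receipt of the image".

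**Recording and follow-up.** Section 8.2 records all adverse effects and abnormal test findings, whatever their suspected cause. Its follow-up commitment is narrower: "Adverse effects or abnormal test findings felt to be associated with the investigational device", or with another study product, "will be followed until the effect (or its sequelae) or the abnormal test finding resolves or stabilizes at a level acceptable to the sponsor-investigator". The pause rule in 8.5 covers death, life-threatening events and other serious events, among them "disability or clinically significant manifestation of local hemorrhage or edema) due to the procedure". For incidental findings, 8.6 adds: "Incidental findings of clinical significance and the management of such findings should be documented in the research records of this study". At continuing review the IRB receives, among other items, "a description of the incidental finding of clinical significance, the date of communication with the subject and the outcome, if known".

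**After withdrawal.** Section 4.4.2 says only that follow-up depends on when the subject withdrew.

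**Analysis.** Section 7.3 defines one population. Its members must have been randomized, have received the device, and have met every processing requirement of the protocol. Section 5.3 describes a single-arm trial without randomization. Section 3.4 assesses safety by MRI and neurocognitive tests. Section 7.1 calls the method successful if the blood-brain barrier (BBB) is safely opened in at least 75% of cases, and does not define cases.

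**The concern.** Membership of the only defined analysis set can depend on the outcome that the trial is meant to measure. A treated subject with a new post-FUS scan finding may be withdrawn for it under 8.6. With no commitment in 4.4.2 to later visits, that subject may then fail the compliance condition in 7.3.

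Two things are at stake. The first is the safety result and the 75% success rate, which could be computed without the subject who had the finding. The second is the three-week and three-month cognitive, PET and blood data. Section 6.4 schedules those visits to assess long-term safety, and 8.6.1 acknowledges that long-term effects in the human brain have not been studied.

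The *randomized* condition is a separate defect in the same sentence. Read literally, nobody in this trial qualifies, so 7.3 cannot be applied as written even when no subject is withdrawn.

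**Working it through.** **1. The plan's own figure.** Section 7.1 gives a difference of 200 mm³, SD 50 mm³, α = 0.05, power 0.95 and at least 6 subjects. Taking 50 as the SD of the paired difference (an assumption), d = 200/50 = 4. The exact two-sided paired t-test has power 0.909 at n = 3, 0.998 at n = 4 and above 0.999 at n = 5. If 50 is instead the SD of each scan with no correlation, d = 200/(50√2) = 2.83, with power 0.950 at n = 4 and 0.995 at n = 5. Six is therefore enough, and losing one subject hardly affects power. The issue is selective loss.

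**2. The path of one treated subject.**
- A new finding appears on a post-FUS scan. Section 8.2 records it.
- If it is felt to be associated with the device or another study product, 8.2 follows it to resolution or stabilization.
- If it is labelled incidental, 8.6 (or 8.6.1) withdraws the subject. No section says which route governs a finding that is new after FUS.
- Once withdrawn, the subject has no assured later visits (4.4.2) and may fail the compliance condition (7.3).

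**3. Which data are exposed.** The day-3 MRI falls on day 2 to 4, and the three-week visit on day 21 ± 7, that is day 14 to 28. A same-day MRI received on day 0 must be read by day 14, and the day-3 MRI by day 2 + 14 = 16 to day 4 + 14 = 18. If a same-day finding is read at once, the day-3 MRI is also exposed. If it is read later, that MRI may already have been done, and the three-week and three-month visits are what remain. A finding on the three-week PET exposes only the three-month visit.

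**4. Safety count (assumed data).** One of six treated subjects has a new finding. Exact (Clopper-Pearson) 95% limits:
- All treated, 1/6 = 16.7%: lower limit 1 − 0.975^(1/6) = 0.0042; upper limit solves (1 − p)^6 + 6p(1 − p)^5 = 0.025, giving p = 0.641.
- Subject left out, 0/5: lower limit 0; upper limit 1 − 0.025^(1/5) = 0.522.

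**5. The 75% criterion (assumed data).** With six as denominator, 0.75 × 6 = 4.5, so 5 successes are needed. With five, 0.75 × 5 = 3.75, so 4 are needed. Suppose that the BBB opens in five of six and one of those five has the finding.

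| Subject with the finding | All six kept | Subject excluded |
|---|---|---|
| Not counted as safely opened | 4/6 = 67%, misses | 4/5 = 80%, meets |
| Still counted as a success | 5/6 = 83%, meets | 4/5 = 80%, meets |

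Excluding one non-success changes the result only when there are exactly four successes. With 0 to 3 the criterion is missed either way (3/5 = 60%), and with 5 it is met either way.

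**The case against.** Several stronger readings are tempting, and the documents do not support them.

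- **The event would vanish.** It would not. Section 8.2 records every abnormal finding regardless of suspected cause, 8.3.2 sends unanticipated adverse device events to the IRB within 2 business days, and 8.6 documents and reports clinically significant incidental findings.
- **Findings from before FUS are mishandled.** They are largely dealt with at screening. Section 4.1 finalizes enrollment after the MRI, 4.2 excludes tumors and hemorrhages, and 6.1 gives the first MRI a screening purpose. The gap matters mainly after FUS.
- **Section 8.6 contradicts 8.2 and 8.5.** It need not. If *incidental* means unrelated to FUS, the routes are compatible. A new lesion at the target is what the post-FUS MRIs look for, and 8.5 lists local hemorrhage and edema as severe adverse effects. Against that, 8.6 names subarachnoid hemorrhage as incidental, right after the sentence on follow-up scans. This calls for reconciliation but does not prove a contradiction.
- **Withdrawal stops data collection, or safety is reported only in the 7.3 set.** Neither is stated. Section 4.4.2 is vague, and 7.3 is not tied to 3.4 or 7.1. Equally, no section says that every treated subject is counted.
- **The success verdict is likely to be wrong.** The same-day MRI that shows opening is acquired before any post-FUS withdrawal. The change from 4/6 to 4/5 also requires that the excluded subject be a non-success, and a finding treated as unrelated might not make the opening unsafe. The chance of exactly four successes in six, at any assumed success rate, is not the probability of this problem.

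It is also fair that, with six subjects, each can be listed individually. A listing would show the finding but would not settle the denominator or supply later data that were never collected.

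**Conclusion.** The point holds in limited form. Followed as written, the plan allows a treated subject to leave the analysed results, and to miss the three-week and three-month assessments, because of a safety finding. It requires neither. That outcome depends on three conditions: the finding is labelled incidental, later data are not collected, and withdrawal counts as non-compliance under 7.3.

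Under those conditions one exclusion turns 1/6 into 0/5. It changes the 75% result only if the subject is also a non-success and there are exactly four successes. These are illustrations on assumed counts; the documents give no probability of such an event. The *randomized* condition in 7.3 is wrong for this design whatever happens with withdrawals. The problem merits correction, mainly because the remedy is less open to bias and costs only wording.

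**What to change.** 1. **Section 7.3.** Delete the randomization condition. Define the safety and primary analysis set as every subject who received FUS. Use it for the MRI and neurocognitive safety endpoint (3.4) and as the denominator of the 75% criterion (7.1). Keep the compliant set as supplementary only.
2. **Safety reporting.** In that set, report all new post-FUS findings whatever their label, with attribution alongside. Exempt the expected gadolinium enhancement at the target that represents BBB opening; otherwise every success would count as a safety finding. Interpret other findings seen only with contrast cautiously, because the baseline MRI is without gadolinium.
3. **Section 4.4.2.** State that already scheduled safety data continue to be collected after withdrawal as far as consent and the treating clinician's judgment allow.
4. **Sections 8.2, 8.5, 8.6 and 8.6.1.** Reconcile them on what *incidental* means and which section governs a finding new after FUS. No withdrawal rule is proposed here, and referral for care is unchanged.

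The cost is wording, with no added visits or scans. The downside is that some later data may still be missing and must be reported as such, and some counted findings may be unrelated to FUS.
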